10.3.3 Exploratory Efficacy Analyses

The exploratory endpoints, including the change in IGA and FASI from week 26 to follow-up, will be analyzed in the same manner as the appropriate secondary endpoints. The p-values from these comparisons will not be reported but the differences between each dose group and placebo will be summarized as odds ratios or mean differences as appropriate with 95% confidence intervals.

10.3.4 Additional Analyses

A sensitivity analysis will be conducted using the Per-Protocol (PP) population to assess the robustness of the results for the primary endpoint.

An additional sensitivity analysis of the primary endpoint will be conducted in the portion of the ITT who complete the 26 week treatment period and have a 26 week assessment, if this population differs from the PP population.

A further sensitivity analysis will be conducted in which those patients who do not provide data at 26 weeks will be considered as treatment failures.

Analyses and summaries of the primary endpoint will also be presented by subgroup. These will include gender, age, site and baseline IGA score groups. As the sample sizes of subgroups are likely to be small,

these analyses will be presented for information purposes only, and statistically significant results are not anticipated.

10.3.5 Safety Endpoints

AEs will be collected for all randomized participants and will be listed with type of AE, severity and relationship for each treatment group, using the safety population. Adverse event data will be summarized for each treatment groups using frequencies and percentages (% of participants with each specific AE). If frequencies permit, Chi-square tests or fisher's exact tests may be used to compare the rates of occurrence between treatment groups. Known AEs specific to oral or topical rapamycin will be individually summarized by treatment group.

Between-treatment comparisons will be made for changes in vital signs, hematology, biochemistry, blood lipids and urinalysis from baseline at visits V1-5. Baseline is defined as the last pre-treatment assessment, whether obtained at screening, randomization or V0. Changes between V5 and Follow-up will also be examined.

Blood rapamycin concentrations will be summarized for each of the treatment groups at all scheduled timepoints using standard descriptive statistics (means, medians, geometric means, ranges, standard deviations and standard errors), as appropriate.

Adverse events will be monitored up to 4 weeks after administration of the final dose of study medication.

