2 TRIAL OBJECTIVES

2.1 Hypothesis

It is hypothesized that the two strengths of *Rapamycin cream, topical* will improve the appearance of FA associated with TSC compared to placebo. It is also expected that both strengths will be well tolerated.

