2.3 Safety Objective

The Safety Objective of the study is to determine and compare the incidence of treatment-emergent adverse events (TEAEs) over the course of the study among the three treatment groups.

The incidence of known topical rapamycin side effects (e.g. treatment area irritation, dryness, and redness) and oral rapamycin side effects (e.g. hypersensitivity reaction, angioedema, fluid retention, wound healing disturbance, hyperlipidemia and renal function aggravation (etc.) and will be individually summarized by treatment group.

Planned hospital admissions and/or surgical operations for an illness or disease which existed before the drug was given or the participant was randomized in a clinical study will not be considered adverse events.

In addition, a physical examination, vital signs, hematology, biochemistry, blood lipids and urinalysis will be assessed at screening, at each visit (V1-5), and at follow-up to determine if there are any clinically significant changes. Blood rapamycin concentration will also be determined at screening and at each visit (V1-5) and at follow-up to investigate systemic absorption of the drug product.

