6.2.1 Evaluations of Specific AEs

Known topical rapamycin adverse events will be compared between groups:

- Treatment area irritation (e.g. erythema, papules, vesicles, erosion etc.)
- Treatment area dryness

Known oral rapamycin adverse events will be compared between groups:

- Hypersensitivity reactions
- Angioedema

- Fluid retention
- Wound healing disturbance
- Hyperlipidemia
- Renal function decline
- Proteinuria
- Infections

CRFs will not specifically list these adverse events but they will be separated for analysis.

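### Section 10.3.5 plans no between-group difference or confidence interval for any adverse event, although the safety objective is to compare incidence among groups

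*Combined protocol and SAP*

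**What the plan says.** Section 2.1, under the heading Hypothesis, adds a tolerability expectation: "It is also expected that both strengths will be well tolerated". It attaches no rate, margin or test.

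Section 2.3 sets the objective: "The Safety Objective of the study is to determine and compare the incidence of treatment-emergent adverse events (TEAEs) over the course of the study". The comparison is among the three treatment groups.

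Section 6.2.1 is equally firm on the named effects: "Known topical rapamycin adverse events will be compared between groups". It says the same of the known oral effects and names no method for either.

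Section 10.3.5, with the same text in the synopsis under Statistical Methods, is where the analysis is defined. The committed output is descriptive: "Adverse event data will be summarized for each treatment groups using frequencies and percentages". The only comparative method is optional: "If frequencies permit, Chi-square tests or fisher's exact tests may be used to compare the rates of occurrence between treatment groups". The known rapamycin effects are to be summarised by group; the promise to compare them is not repeated. Changes in vital signs and laboratory values are to be compared between treatments, with no method, estimate or interval named.

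Section 10.3.3 does the opposite for exploratory efficacy. P-values are withheld and the differences from placebo are "summarized as odds ratios or mean differences as appropriate with 95% confidence intervals". Section 10.3.1 likewise gives an odds ratio and 95% confidence interval for the exploratory comparison of the two doses.

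**The concern.** An objective to compare incidence calls for an estimate of the difference and a statement of its precision. The plan supplies neither for adverse events, so a stated trial objective gets less than an exploratory efficacy endpoint.

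If the optional test is run, its p-value is the only inferential result for adverse events. The trial was sized for a 10% versus 40% efficacy contrast, so a smaller excess of irritation, infection, hyperlipidaemia or proteinuria would often be non-significant. A report could then say that no significant difference from placebo was found, without showing that the same data allow a large excess.

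There is also a wording mismatch: 6.2.1 says comparisons will be made, while 10.3.5 says tests may be used.

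**Working it through.** **Inputs from the documents.** 40 per group (section 10.2), 1:1:1 allocation (section 5.3), chi-square or Fisher for adverse events (section 10.3.5).

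**Assumptions, because the documents are silent.** Adverse-event rates; two-sided alpha of 0.05 without multiplicity adjustment; each test compares one dose with placebo; all 40 per arm are treated.

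**Step 1: the plan's own figure.** Section 10.2 gives 40 per group for 10% versus 40%, alpha 0.025, power above 80%. Taking two-sided alpha and pooled variance under the null:

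n = [z(0.9875)·√(2·p̄·(1−p̄)) + z(0.80)·√(p1(1−p1) + p2(1−p2))]² / (p2−p1)²

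With p̄ = 0.25: n = [2.241·√0.375 + 0.842·√(0.09 + 0.24)]² / 0.30² = 38.3, so 39 per arm. Power at 40 is 82.0%. The stated figure reproduces. It concerns efficacy only; no power or precision is stated for adverse events.

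**Step 2: chance of missing a true difference.** For all 41 × 41 possible outcomes, sum Bin(i; 40, p_placebo) × Bin(j; 40, p_active) over those with p ≤ 0.05, and subtract the sum from 1.

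| Placebo vs active (assumed) | Fisher misses | Uncorrected chi-square misses |
|---|---|---|
| 5% vs 10% | 96% | 85% |
| 5% vs 15% | 82% | 65% |
| 5% vs 20% | 59% | 43% |
| 10% vs 20% | 84% | 75% |
| 10% vs 30% | 47% | 37% |
| 10% vs 40% | 15% | 10% |
| 20% vs 40% | 59% | 50% |
| 30% vs 60% | 28% | 20% |

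A doubling is missed by Fisher anywhere from 28% to 96% of the time in this table, depending on the placebo rate, so no single figure describes the design.

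**Step 3: what an interval would show.** Newcombe's method combines the Wilson limits (l, u) of each arm:

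lower = d − √[(p1−l1)² + (u2−p2)²]; upper = d + √[(u1−p1)² + (p2−l2)²]

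- 6/40 vs 2/40: p1 = 0.150 (Wilson 0.0706 to 0.2907), p2 = 0.050 (0.0138 to 0.1650), d = 0.100. Lower = 0.100 − √(0.0794² + 0.1150²) = −0.040. Upper = 0.100 + √(0.1407² + 0.0362²) = 0.245. Fisher p = 0.26.
- 4/40 vs 4/40: both Wilson intervals are 0.0396 to 0.2305, d = 0. Limits = ±√(0.1305² + 0.0604²) = ±0.144. Fisher p = 1.0.

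So identical counts in both arms still allow an excess of about 14 points, which a p-value of 1.0 does not convey.

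**Step 4: the open choice of test.** For 8/40 vs 2/40, Fisher gives p = 0.087 and uncorrected chi-square p = 0.043. The plan names both tests and gives no rule for choosing between them. The Newcombe interval is 0.1 to 30.2 points, which agrees with chi-square. The disagreement therefore reflects Fisher's conservatism, not information lost by omitting an interval.

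**The case against.** The best defence is that adverse events in a trial sized for efficacy are properly reported descriptively. The committed outputs are counts and percentages by arm, listings by severity and relationship, and individual summaries of the known rapamycin effects. Section 6.2.2 bases the overall evaluation on all observed events and on clinically significant changes compared among the groups, and section 6.2.3 adds blood concentrations. The test is optional. A reader can compute a risk difference and its interval from the published counts, and section 10.6 allows added analyses if they are disclosed.

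Most of this stands, and it rules out several stronger readings that a reader might infer:

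- **That a tolerability statement could rest only on non-significance.** The plan nowhere says that a p-value above 0.05 means safe, and section 6.2.2 describes a clinical, descriptive judgement.
- **That 59% to 84% is how often the design misses any doubling to quadrupling.** Those two figures belong to Fisher's test at 5% vs 20% and 10% vs 20%, which are assumed rates. The other named test gives 43% and 75%, and other placebo rates move the figure widely.
- **That uncommon events go uncompared.** They may lose a test; counts and percentages by arm remain.
- **That laboratory comparisons are limited to p-values.** Section 10.3.5 names no method, so it neither limits them to p-values nor plans an interval.
- **That intervals would cure low power.** They would not.

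The defence does not explain why sections 2.3 and 6.2.1 promise comparison while 10.3.5 plans no comparative estimate, or why exploratory efficacy gets one and safety does not.

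**Conclusion.** The point holds as a minor gap between objective and analysis. The documents commit to comparing adverse-event incidence and plan no difference or interval for it. This follows from the text and needs no assumption.

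The size of the consequence does rest on assumptions. With 40 treated per arm, pairwise two-sided tests at 0.05 and 20% on active, Fisher misses the excess 59% of the time when placebo is 5% and 84% when it is 10%; uncorrected chi-square misses it 43% and 75%. These illustrate how little a non-significant result would mean and are not forecasts. The intervals in Step 3 depend only on the counts shown: upper limits of 24.5 points for 6/40 vs 2/40 and 14.4 points for 4/40 vs 4/40.

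The efficacy analysis and the sample size are unaffected.

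**What to change.** In section 10.3.5 and the matching synopsis paragraph, replace the sentence on optional tests with text such as:

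> For any TEAE, any SAE, TEAEs leading to discontinuation, and each category named in section 6.2.1, the difference in percentage of patients between each dose and placebo will be given with a 95% confidence interval (Newcombe or Miettinen-Nurminen). Non-significance will not be used to conclude tolerability.

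For vital signs and laboratory values, give the mean difference from placebo in change from baseline with its 95% confidence interval, as 10.3.3 does for exploratory efficacy. The new text also reconciles 10.3.5 with the promise of comparison in 6.2.1. A row pooling the two doses is optional; it assumes a shared risk, so it should sit beside the per-dose rows and not replace them.

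The cost is a wording change and a few table columns, with no new patients or data. The intervals will be wide, so the tolerability statement will look less favourable, and the change adds no power.

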10.3.6 Demographic and Background Characteristics

Participant demographic and background characteristics will be descriptively summarized by treatment group using means, medians, standard deviations, ranges, frequencies and percentages as appropriate. No formal statistical comparisons will be made between treatment groups.

10.4 Treatment Compliance

To evaluate the degree of treatment compliance during the trial, tabular summaries of study drug usage will be presented for each randomized group.

Participants whose study drug usage exceed the limitations provided by the study protocol will be included in a list of protocol deviations. The potential effect of such deviations on the resulting clinical evaluations will be discussed in the study report.

10.5 Missing data

Every effort will be made to obtain all assessments at the appropriate time points from all randomized participants, especially to obtain assessments from early withdrawals. Where early withdrawals occur between visits without a visit to confirm subject withdrawal, assessments completed at the visit preceding withdrawal will be considered the assessment at discontinuation/withdrawal.

For the exploratory analyses, intermittent missing values in the analysis of IGA, FASI and percentage improvement scores will be imputed by linear interpolation of adjacent scores (i.e. immediately preceding and immediately following the missing value). No attempt will be made to impute missing data for Overall Improvement/Patient Satisfaction (recorded only at V5, or at last visit where withdrawal was confirmed).

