Brief Description	
The study can be divided into a Screening Phase, a Treatment Phase and Follow-up.
 
The Screening Phase includes collection of Informed Consent and the assessment of the subjects' suitability for the study. Eligible subjects will be assigned a unique randomization number before the first application of the study drug. Subjects will be randomized to receive treatment with one of two strengths of Rapamycin cream, topical (0.5% and 1.0% rapamycin, respectively) or placebo.
 
The Treatment Phase of the study comprises one clinical visit at baseline (V0) and 5 subsequent clinical visits after 2, 8, 14, 20 and 26 weeks treatment (V1-5) with Rapamycin cream, topical or placebo. The amount of cream will be based on the total area of the facial lesion(s) and patients will be instructed to apply the formulation every evening, about half an hour before retiring for bed, for 26 weeks.
 
Follow-up will be performed 28 days after the V5 visit, or the last visit where early withdrawal from treatment was confirmed.
 
Assessment of the extent and severity of facial angiofibroma will be performed at randomization, at each clinical visit (V1-5) and at follow-up using a variety of measures including an Investigator's Global Assessment (IGA) scale, the facial angiofibroma severity index (FASI), as well as subjective and objective improvement ratings.
 
The primary efficacy endpoint is based on the IGA scale, described below:
 
  
 Grade	Short Description	Detailed Description	
   
 0	Clear	No signs of facial angiofibroma	
  
	Grade	Short Description	Detailed Description	0	Clear	No signs of facial angiofibroma
Grade	Short Description	Detailed Description					
0	Clear	No signs of facial angiofibroma					

1	Almost Clear	Few small angiofibromas (< 2 mm); normal to pink coloration in affected area*
2	Mild	Predominantly small angiofibromas (< 2 mm) with few intermediate tumors (2-4 mm); pink to red coloration in affected area
3	Moderate	Predominantly intermediate angiofibromas (2-4 mm) with few large tumors (> 4 mm); red coloration in affected area
4	Severe	Mix of intermediate (2-4 mm) and large angiofibromas (>4 mm) present diffusely on face; intense and generalized redness on the whole face

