1.2 Study Drug Rationale

Rapamycin is a macrolide antibiotic compound produced by *Streptomyces hygroscopicus* that was first isolated from a soil sample from Easter Island, also known as Rapa Nui. Rapamycin ligates with the immunophilin FK506 binding protein-12 creating a complex that inhibits the activation of the mTOR. mTOR is a protein kinase that regulates cell growth and cell proliferation (17). Rapamycin is currently commercially available only as an oral solution or as a tablet (e.g. Rapamune[®]). The currently approved indication for rapamycin is for the prophylaxis of organ rejection in patients aged ≥ 13 years receiving renal transplants (maintenance immunotherapy) and for the treatment of patients with lymphangioliomyomatosis (LAM), a rare, cystic lung disease (18).

Due to its potent antiproliferative effects, rapamycin has also been investigated as a treatment for a series of cutaneous diseases including FA associated with TSC. Interest in the use of rapamycin for the treatment of FA began after the publication of a case report of a 21 year old TSC patient that underwent kidney transplant. After initial immunosuppression with tacrolimus, the patient was transferred to *oral rapamycin* therapy, during which time her FA improved dramatically (19).

There is an extensive literature which supports the efficacy and safety of various topical rapamycin formulations for the treatment of FA. In the last 7 years, 11 clinical trials and 17 case reports/observational studies have been published in the literature. Overall, the outcomes obtained by the vast majority of patients in these studies demonstrate that topical rapamycin has potent efficacy for FA associated with TSC (19–43). It is difficult to determine the impact of different treatment frequencies in terms of efficacy (i.e. twice daily or 3 times per week) but one study noted that a twice daily treatment regimen could be replaced by a once daily regimen without loss of efficacy (37). In line with the progressive nature of the disease, there is some data that demonstrates that the positive effect diminishes after treatment is stopped (1,45).

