2.2 Efficacy Objectives

The Efficacy Objectives of the study are to determine and compare the efficacy of two different strengths of *Rapamycin cream, topical* and placebo over 26 weeks of once-daily treatment.

The primary efficacy endpoint is the percentage of patients obtaining successful treatment after 26 weeks or at discontinuation/withdrawal, based on the blind assessment using the IGA scale. Success is defined as clear or almost clear with an improvement of at least two grades from baseline, i.e. 2 to 0; 3 to 1.

The secondary efficacy endpoints are:

1. Time to treatment success
2. Change from baseline in IGA after 26 weeks treatment or at last visit if early withdrawal/discontinuation
3. Change from baseline in FASI after 26 weeks treatment or at last visit if early withdrawal/discontinuation
4. Subjective (patient or parent/caregiver) improvement rating from first visit (V0) after 26 weeks treatment or at last visit if early withdrawal/discontinuation
5. Objective (clinician) improvement rating from first visit (V0) after 26 weeks treatment or at last visit if early withdrawal/discontinuation
6. Categorical Improvement of Facial Angiofibroma from first visit (V0) after 26 weeks treatment

In addition, exploratory efficacy endpoints are:

1. The percentage of patients with successful treatment according to IGA scale after 2, 8, 14 and 20 weeks treatment
2. Change from baseline in IGA after 2, 8, 14 and 20 weeks treatment
3. Change from baseline in FASI after 2, 8, 14 and 20 weeks treatment
4. Change from baseline in each FASI component (erythema, size, extension) after 2, 8, 14, 20 and 26 weeks treatment
5. Subjective (patient or parent/caregiver) improvement rating from first visit (V0) after 2, 8, 14 and 20 weeks treatment
6. Objective (clinician) improvement rating from first visit (V0) after 2, 8, 14 and 20 weeks treatment
7. Change in IGA from week 26 to Follow up (4 weeks after final dose)

8. Change in FASI from week 26 to Follow up (4 weeks after final dose)

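### Section 10.5 lets a missed week-26 IGA or FASI be interpolated from the off-treatment follow-up score, which distorts the exploratory week-26-to-follow-up change in those patients

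*Combined protocol and SAP*

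**What the plan says.** Section 10.5 sets the imputation rule: "For the exploratory analyses, intermittent missing values in the analysis of IGA, FASI and percentage improvement scores will be imputed". The method is that they are "imputed by linear interpolation of adjacent scores (i.e. immediately preceding and immediately following the missing value". The only exception named is the overall improvement/satisfaction item, which is not imputed. Nothing is said about which study phase the neighbouring scores may come from.

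Three exploratory endpoints in section 2.2 use a week-26 score:
- Endpoint 4: "Change from baseline in each FASI component (erythema, size, extension) after 2, 8, 14, 20 and 26 weeks treatment".
- Endpoint 7: "Change in IGA from week 26 to Follow up (4 weeks after final dose").
- Endpoint 8: "Change in FASI from week 26 to Follow up (4 weeks after final dose").

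Section 10.3.3 confirms that endpoints 7 and 8 belong to the exploratory analyses: "The exploratory endpoints, including the change in IGA and FASI from week 26 to follow-up, will be analyzed in the same manner" as the matching secondary endpoints. They are reported as estimates with 95% confidence intervals and without p-values.

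The Synopsis describes "5 subsequent clinical visits after 2, 8, 14, 20 and 26 weeks treatment (V1-5"), so week 20 (V4) is the visit before week 26 (V5). Table 3 and sections 7.2.2 and 7.3 show both scales scored at V1 to V5 and again at follow-up. Section 3 places follow-up 28 days after V5.

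**The concern.** When the V5 score is missing but V4 and follow-up are present, the score that immediately follows the gap is the follow-up score, taken about four weeks after the cream was stopped. The filled week-26 value already contains part of any off-treatment change. Endpoints 7 and 8 then subtract it from that same follow-up score, so follow-up sits on both sides of the difference.

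Linear interpolation also assumes a straight line through the point at which treatment stops. Section 1.2 gives a reason to doubt that: "there is some data that demonstrates that the positive effect diminishes after treatment is stopped".

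Endpoints 7 and 8 are the only named efficacy endpoints that look at what happens after stopping. In a patient who was stable or improving up to week 26, the rule tends to hide loss of effect. That matters mainly in the active arms, where there is an effect to lose. For endpoint 4, a value built partly from off-treatment data would be presented as a week-26 on-treatment result.

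**Working it through.** The plan gives no figure of its own on this point, so there is none to reproduce.

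**Inputs.** V4 at week 20 and V5 at week 26 (Synopsis, Table 3). Follow-up at nominal week 30, which is 28 days after V5 (section 3). Windows of ±3 days for V4 and ±5 days for follow-up (Table 3). Higher scores are worse, so a positive change from week 26 to follow-up is loss of benefit.

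**Filled value.** Write S20, S26 and S30 for the three scores.
- Time-weighted: S26* = S20 + (6/10)(S30 − S20) = 0.4·S20 + 0.6·S30.
- Endpoint 7 or 8 becomes S30 − S26* = 0.4·(S30 − S20).
- If interpolation is read as the plain mean, it becomes 0.5·(S30 − S20).
- The true S26 appears in neither expression.

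**Visit windows.** Take V5 at day 182, V4 at days 137 to 143 and follow-up at days 205 to 215. The factor 0.4 then ranges from 1 − 45/68 = 0.34 to 1 − 39/72 = 0.46.

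**Ratio to the truth.** Let D = S30 − S26 (true change, D > 0) and g = S26 − S20 (change from week 20 to 26; negative means improving). Imputed/true = 0.4·(1 + g/D), or 0.5·(1 + g/D) with the mean. At least half is lost when g ≤ 0.25·D (time-weighted) or g ≤ 0 (mean). Stable or improving patients (g ≤ 0) meet both conditions. At g = −D the change is erased; below that it reverses.

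**Examples** (week 20, week 26 in brackets because missed, follow-up):

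| Scores | True change | Time-weighted | Plain mean |
|---|---|---|---|
| IGA 1, (1), 2 | +1 | +0.4 | +0.5 |
| IGA 2, (1), 2 | +1 | 0 | 0 |
| IGA 3, (1), 2 | +1 | −0.4 | −0.5 |
| FASI 5, (4), 6 | +2 | +0.4 | +0.5 |
| IGA 1, (2), 3 | +1 | +0.8 | +1.0 |
| IGA 1, (2), 2 | 0 | +0.4 | +0.5 |

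The last two rows are patients who worsened before week 26. One loses 20% or nothing, and the other acquires a change that did not occur.

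**All integer IGA patterns (0 to 4) with a true rebound.** With no worsening from week 20 to 26 there are 40 patterns: 20 shrunk by at least half, 10 erased, 10 reversed. With worsening there are 10 patterns, and none is shrunk by half or more. These count score patterns; they are not patient frequencies.

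**Arm level, illustration only.** Assume a true mean rebound of 1.0 FASI point, a proportion m filled this way, and drift d from 0 to −0.4 point between weeks 20 and 26. The arm mean is (1 − m)·1.0 + m·0.4·(1.0 + d).
- m = 5%: 0.95 + 0.05·0.4·(0.6 to 1.0) = 0.96 to 0.97.
- m = 10%: 0.90 + 0.10·0.4·(0.6 to 1.0) = 0.92 to 0.94.
- m = 20%: 0.80 + 0.20·0.4·(0.6 to 1.0) = 0.85 to 0.88.

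**The case against.** The rule may have been written with gaps inside the treatment phase in mind. It covers percentage improvement together with IGA and FASI, and percentage improvement is not collected at follow-up, so a missed V5 value on that scale could never be interpolated. Exploratory endpoints 1, 2, 3, 5 and 6 all fall at weeks 2 to 20, where the next scheduled score is on treatment. This stands as evidence of likely intent. It does not change what the text permits: for IGA and FASI the next recorded score after a missing V5 is follow-up, and endpoints 4, 7 and 8 are exploratory.

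The triggering patient is uncommon: no V5 score, not an early withdrawal, follow-up attended. Withdrawals are largely outside the rule, because their follow-up is timed from the visit confirming withdrawal, and the preceding visit stands in if there was none. The date is also less certain than week 30 suggests. Section 3 and section 7.3 tie follow-up to V5, to the visit confirming withdrawal or to the last treatment-phase visit, and only the Table 3 heading ties it to the final dose. For a patient who skipped V5 altogether, the factor 0.4 is therefore nominal. All of this stands and limits the reach.

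A reader might infer that every filled patient is biased toward zero, or loses at least half of the change. The documents do not support that: the result depends on the course from week 20 to 26, and worsening before week 26 can leave the change intact or create one. Nor do they support a stated rebound at four weeks. Section 1.2 speaks only of some data, and the study of stopping treatment in Table 1 had 6 to 9 months off treatment.

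**Conclusion.** The point holds with its conditions attached. As written, the rule does not stop a missing week-26 IGA or FASI from being filled from week 20 and follow-up. Endpoints 7 and 8 then carry 0.4 (or 0.5) of the follow-up-minus-week-20 difference and no information about week 26. Whether the true change is hidden, reversed, preserved or invented depends on what happened between weeks 20 and 26.

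This is a minor point. It affects exploratory estimates reported without p-values, in patients who lack a V5 score but attend follow-up. The imputation rule is confined to the exploratory analyses, so it would be wrong to carry the concern over to the primary or secondary endpoints. The arm-level range of 0.85 to 0.97 for a true 1.0-point rebound rests wholly on assumptions: 5% to 20% missed, 0 to 0.4 point of late improvement, and the rebound itself. It shows the order of magnitude and is not a forecast.

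**What to change.** Add to section 10.5 that follow-up scores are never used to interpolate a treatment-phase visit, and that exploratory endpoints 7 and 8 and the week-26 FASI component changes use observed week-26 scores only. This takes one sentence in the plan and one condition in the imputation program. Section 10.6 allows missing-data handling to change later with disclosure in the study report, but settling it now avoids a choice made after seeing data.

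The cost is a slightly smaller sample for these summaries. They also become complete-case summaries, so they rely on patients with an observed V5 being representative of those without one. The report should give the number excluded in each arm so that readers can judge this.
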